We propose a pilot and feasibility trial to use continuous glucose monitoring (CGM) in youth with type 2 diabetes (T2D) and public insurance. This feasibility trial would fill a gap in the literature with respect to CGM use in youth with type 2 diabetes. The findings from this trial can provide much needed data to pave the way for future studies using CGM technology in this population. Our proposal is focused on youth with public insurance, seeking to provide diabetes technology for patients and their families to use in daily diabetes management. This pilot is an expansion of our existing program of CGM access to youth with type 1 diabetes which has led to an improvement HbA1C of 0.5% over 1 year and positive feedback from patients and families.^{1,2}

Specific Aim 1: Evaluate the feasibility of CGM start and continuation in youth with T2D and describe glucose metrics and patient reported outcomes (PROs). We will pilot and refine a program to test the hypothesis that CGM start and continuation in youth with T2D is feasible and then evaluate glucose metrics and PROs.

Hypothesis 1a: In phase 1, CGM use exceeding >50% of participants will be feasible and sustainable in youth with T2D, measured by days of CGM use per 2-week period (>75%). **H1b:** Following an additional needs assessment after phase 1, in phase 2 sustained CGM use per 2-week period (>75%) will exceed 75% of participants. **H1c:** Based on completion of PROs surveys, it is expected that diabetes-specific distress will decline, and overall well-being/quality of life will improve. Secondary outcome PROs (see protocol synopsis) collected at baseline will be associated with HbA1c and diabetes management outcomes. Data on glucose metrics, SDOH, and needs and barriers will be described.

Specific Aim 2: To assess the clinical outcomes (HbA1C, time in range [70-180 mg/dL], time in hypoglycemia [<70 mg/dL]) of individuals participating in this trial compared to clinic historical controls.

Hypothesis 2: Use of CGM will improve HbA1C and other clinical metrics of diabetes glucose control.

Measured Outcomes:

1. Sustained use of CGM by patients over one year measured by days of CGM use per every 2-week period with >80% as goal.
2. Change in HbA1C over first year of CGM use
3. Glucose profile metrics: percentage time in range, time in hypoglycemia, and time in hyperglycemia obtained from CGM.
4. Change in weight and BMI over first year of CGM use using clinic visit weight and BMI measurements.
5. PROs

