Significant improvements in HbA1C have been shown in youth with type 1 diabetes with public insurance with uninterrupted CGM use.²² This real-world data in youth with type 1 diabetes has complimented research study data and paved the way for earlier and easier CGM approval for youth, particularly publicly insured youth.

Our team has shown that youth with T1D with public insurance who have uninterrupted CGM use compared to those who lose CGM coverage due to insurance issues have significant improvements in HbA1c^{22,23}. This real-world data in youth with T1D has complimented research study data and paved the way for earlier and easier CGM approval for youth, particularly publicly insured youth. We aim to translate these learnings to our T2D population. In our clinic, youth with T2D have a mean HbA1c of 8.6% with only 35% at goal HbA1c of <7% (n=311 HbA1c values), indicating that the majority of youth with T2D are not meeting this significant diabetes therapy goal. Reflective of the national data demonstrating youth with T2D are overwhelmingly minorities and from families of lower SES, a significant portion of our T2D patient population (n=131) is publicly insured (77%), minority status (73% and Latinx 66%), and has Spanish-speaking parents or guardians (56%), all groups which have lower rates of diabetes technology use^{11,24}.

Design: This will be a two-phase pilot program focused on youth with T2D to evaluate initiation and sustained use of CGM. The focus of phase 1 will be a feasibility trial to use CGM in 30 youth with T2D and public insurance over a 12-month period. CGM will be provided to all participants. Education for youth and their families about CGM integration in diabetes care will be provided throughout the study. Barriers to CGM adoptions and sustained CGM use will be tracked throughout this phase to inform the further refinement of the program in phase 2 in 50 youth with T2D. As part of closing the disparities in diabetes technology use in youth with T2D, QoL and PROs will be evaluated. The goals of phase 2 are to utilize human factors design data, QoL and PRO metrics collected in phase 1 to address identified needs and barriers to increase initiation and continued use of CGM in this population.

Inclusion criteria

1. Diagnosis of T2D (diabetes autoantibody negative) followed in the Pediatric Endocrinology clinic at Stanford Children's Health

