2. HbA1C greater than 6.5% at enrollment. This is to enroll patients who are working on improving glucose control but are still not meeting HbA1c targets.^{9,25}
3. Interested in starting on a continuous glucose monitor
4. Access to a mobile device that is compatible with CGM applications or willing to use CGM receiver which will be provided. Both the receiver and mobile device allows patients to view glucose data and alerts from the CGM and upload glucose data during or in between in-person or virtual clinic visits, not necessitating that the participant have access to a mobile device.
5. Public insurance
6. Age 4-20 years inclusive

Exclusion criteria

1. Non-T2D diagnosis
2. HgA1C < 6.5%
3. Participant not willing to wear CGM
4. Private insurance

Procedures and Methods

Recruitment: The study team will review clinic schedules to identify youth with T2D from the patients in our clinic who would qualify. The informed consent process will be conducted prior to initiating the study. Following CGM initiation by a CDE, youth will have a routine 1-week clinic follow up with our diabetes team and then will be seen per clinic standard of care, every 3 months thereafter for the 12 months of the study duration. At each visit we will collect descriptive data on CGM use, CGM glucose metrics, and provide CGM supplies. PROs will be evaluated at three time points during the study. In phase 2, we will identify a new cohort of eligible patients who will be evaluated at a similar cadence as phase 1.

Visit	1	2	2a	3	3a	4	4a	5	5a	6
Weeks from start	x	2 weeks	4-6 weeks	12 weeks						
Informed consent and assent Visit Type ** this will be modified if LibreView App is available during study duration, can move visits to TH with lab A1C	x (can be done in person or via TH)									
	In person	IP/TH	phone/IP	IP	phone/IP	IP	phone/IP	IP	phone/IP	IP
Demographics	x									
Diabetes History	x									
HbA1C	x			x		x		x		x
CGM start	x				x					x
PROs	x			x						x
CGM metrics	x	x	x	x		x		x		x
CGM education	x	x	x			x		x		x
CRC check on supplies (confirm use and shipment)	x	x	x	x	x	x	x	x	x	x
Final study visit										x

Visit 1:

- Participants will be offered the opportunity to start on CGM at their scheduled clinic visit
- Participants will receive CGM education from a certified diabetes educator (CDE)

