Problem Areas in Diabetes – Pediatric (Diabetes Burden)	Youth 8-17 and all parents	YOUTH – Youth will complete this survey on psychological distress and burden associated with taking care of diabetes. Child survey for 8-11 years, Teen survey for 12-17 years. PARENTS – complete a proxy version as well as a report of their own distress.
Use of and Comfort with Technology	Youth ≥ 11 , All parents	YOUTH – Youth ages 11-18 will complete this survey on use of and comfort with general technology and diabetes devices. PARENT – All parents complete the same questions on technology and devices.
PROMIS Global Health scale (PGH-7)	Youth ≥ 11	YOUTH – Youth will complete this survey on their overall health, integrating patient experiences across physical, mental and social health

Community Partnership and Engagement

Once complete, results from this study will be shared with medical leadership of California Children's Services (public insurance which provides coverage of diabetes-related care for our youth with type 2 diabetes) at the state and county level to advocate for coverage and access to CGM technology for all youth with type 2 diabetes. We will also engage with the Pediatric Endocrinology Family Advisory Counsel at Stanford Children's Health to combine results from this study with patient/parent advocacy efforts to gain insurance coverage for CGM in all youth with T2D.

Potential Pitfalls and Contingency Plans

Study participants are asked to attend clinic appointments as recommended by their care provider. Our clinic standard is to have patients attend at least 4 visit per year, on average 1 clinic visit every 3 months. There may be missed appointments. Efforts will be made to remind families of appointments the day before the visit by phone or MyChart messaging. If a patient misses an appointment, the team will make efforts to re-schedule the appointment and address barriers to attending clinic appointments.

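### The enrolment HbA1c that admits a patient appears also to be the baseline for HbA1c change, and no control rule is stated, so regression to the mean biases the change toward improvement

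*Combined protocol and SAP*

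**What the plan says.** All references are to the combined protocol and SAP.

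- **Entry.** Inclusion criterion 2 requires "HbA1C greater than 6.5% at enrollment", and exclusion criterion 2 shuts out values under 6.5%. Under Recruitment, "The study team will review clinic schedules to identify youth with T2D from the patients in our clinic who would qualify". No screening visit or separate screening HbA1c is described.
- **Measurement.** The visit table lists HbA1c at Visits 1, 3, 4, 5 and 6. CGM starts at Visit 1, so that is the only value before CGM.
- **Outcome.** Measured Outcomes, item 2: "Change in HbA1C over first year of CGM use". Baseline is not defined. Hypothesis 2 expects improvement.
- **Comparator.** Under Design, "CGM will be provided to all participants". Aim 2 assesses clinical outcomes "of individuals participating in this trial compared to clinic historical controls". The Biostatistical plan does not mention these controls, and their HbA1c range, index date and follow-up are stated nowhere.
- **Analysis.** A mixed model is to describe trajectories and allow for correlation within patients. Regression to the mean is not addressed.
- **Source population.** Preliminary Studies reports that "youth with T2D have a mean HbA1c of 8.6% with only 35% at goal HbA1c of <7" per cent, from 311 values.

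**The concern.** HbA1c varies within a person. A cut-off applied to one reading lets in people who are temporarily above it and keeps out people who are temporarily below it. The admitted group's mean is then expected to be lower at the next reading without any treatment effect. If the admitting reading is also the baseline, that fall is counted as change on CGM. The mixed model does not remove it, because its trajectory starts from the selected value.

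Hypothesis 2 is directional, and the section on community partnership says the results will go to public-insurance leadership to argue for coverage. A fall that is partly selection artefact could mislead that audience, and anyone who plans a later study from it.

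**Working it through.** The plan gives no expected HbA1c effect, SD, correlation or power for this trial, so there is no figure to reproduce. The check asks how large the artefact could be.

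**Inputs from the document.** Cut-off c = 6.5. Clinic mean μ = 8.6, with 35% of values below 7. Background effects for scale only: 0.5 point over one year (the clinic's own type 1 programme, Specific Aims) and 0.4 point (an adult type 2 randomised trial, Background).

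**Assumed.** Within-person correlation ρ between baseline and follow-up, the shape and spread of HbA1c, no CGM effect and no time trend.

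**Formula.** Where the regression of the later on the earlier value is linear, the expected fall among those admitted is

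(1 − ρ) × (E[X | X > c] − μ).

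It is positive whenever ρ < 1. For a normal distribution the second factor is SD × φ(a) / (1 − Φ(a)), with a = (c − μ)/SD.

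**Normal example, SD 2.0.** a = (6.5 − 8.6)/2.0 = −1.05, and the second factor is 0.539.
- ρ = 0.7: 0.3 × 0.539 = 0.16
- ρ = 0.8: 0.2 × 0.539 = 0.11
- ρ = 0.9: 0.1 × 0.539 = 0.05

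A normal curve with mean 8.6 and 35% below 7 would need an SD of 4.15, which is implausible, so skewed shapes were also fitted.

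**Skewed fits.** Shifted gamma and log-normal distributions (lower bounds 4.5, 5.0, 5.3) were solved for mean 8.6 and 35% below 7. Their SDs are about 2.9 to 3.3, and they put 21% to 26% of values at or below 6.5. Pairs were simulated with a Gaussian copula of correlation r. The second row uses gamma fits (lower bounds 4 to 5, formula above) and log-normal fits (lower bounds 0 to 5, simulated).

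| Expected fall, no CGM effect | 0.6 | 0.7 | 0.8 | 0.9 |
|---|---|---|---|---|
| Copula simulation | 0.18–0.35 | 0.13–0.26 | 0.08–0.17 | 0.04–0.08 |
| Wider set of fits | 0.17–0.45 | 0.13–0.33 | 0.08–0.22 | 0.04–0.11 |

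A fall of 0.1 to 0.3 is 25% to 75% of 0.4 (0.1/0.4, 0.3/0.4) and 20% to 60% of 0.5. A fall of 0.04 to 0.08 is 10% to 20% of 0.4.

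**Would qualifying on an earlier value cure it?** With equal correlation between all visits, selecting on a separate earlier HbA1c gives an artefact of about 0 (−0.01 to +0.01). If correlation decays with time, it does not:

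| Assumed correlation at 3 / 12 / 15 months | Same value for both | Earlier qualifying value |
|---|---|---|
| 0.8 / 0.6 / 0.55 | 0.19–0.36 | 0.14–0.24 |
| 0.9 / 0.8 / 0.77 | 0.08–0.17 | 0.06–0.12 |

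The reduction is roughly a quarter to a third.

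**Against sampling error.** With normal SD 2.0 and ρ = 0.7, the SD of change among those admitted is 1.51. At n = 30 the standard error is 1.51/√30 = 0.28, so the bias of 0.16 is about 0.6 standard errors. A two-sided 5% test of no change would reject about 9% of the time. At n = 80 (30 + 50) it would reject about 16% of the time.

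**The case against.** **The dual use is not stated.** No sentence says that the Visit 1 draw is the qualifying value or that it is the baseline, and reviewing clinic schedules is compatible with qualifying on a chart value. This stands. Dual use is a strong inference from the schedule, which is why the point says "appears" only in the reviewer's voice and not as the plan's own rule.

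**Historical controls might cancel the artefact.** They could, if chosen by the same rule. A reader might infer that they would not show the same fall. The documents are silent, and silence does not establish that. What can be said is that nothing requires comparable selection.

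**The size has no anchor.** A reader might infer that the artefact is a large part of the expected effect. The trial states no expected effect, and 0.4 and 0.5 are background figures from other populations. The cut-off lies below the clinic mean and admits about three quarters of values, so selection is mild. At a correlation of 0.9 the artefact is minor. The 311 values also cover all the clinic's youth with type 2 diabetes, seemingly with repeats, and not only the publicly insured.

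**A time trend may run the other way.** The Background describes rapid disease progression in youth, which could raise HbA1c and offset the fall. That is fair, but an uncontrolled change cannot separate the two.

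**This is a pilot.** Aim 1 is feasibility of CGM use, and HbA1c has no success threshold. This limits the importance of the point but does not remove it, because Aim 2 and Hypothesis 2 still draw an HbA1c conclusion.

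**Conclusion.** The concern holds as a bias of known direction and uncertain size. On the most natural reading of the schedule, the one-year HbA1c change starts from a value selected to be above 6.5%, there is no concurrent control, and no stated control rule or analysis step offsets the selection. The expected artefact is about 0.1 to 0.3 point at correlations of 0.7 to 0.8 and 0.04 to 0.08 at 0.9 (up to 0.11 in the wider fits). These figures rest on the clinic-wide distribution, the assumed correlations, no CGM effect and no time trend.

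The documents do not support saying that the artefact would account for most of any observed benefit, or that moving the qualifying value to an earlier visit would abolish it. The point should be addressed before the HbA1c results are interpreted. Confidence is medium, and the feasibility analysis is not affected.

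**What to change.** Add to the Biostatistical plan, for Aim 2 and Hypothesis 2:

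1. Define the qualifying HbA1c and the baseline HbA1c, and say whether they are the same measurement.
2. Select historical controls with HbA1c above 6.5% at an index clinic visit and otherwise the same eligibility. Fix the index visit by a date rule, not by searching a patient's record for a high value, since a search would create a larger fall in the controls.
3. Measure the controls' change from that index value over the same 12 months, or over the same shorter period if the 6-month supply contingency is used.
4. Base the HbA1c conclusion on the between-group difference in change. Report the uncontrolled change descriptively, stating that it is subject to regression to the mean.

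The artefact then becomes common to both groups and cancels to the extent that their HbA1c distribution, within-person correlation and follow-up are alike. Calendar-time differences in care remain a limitation of any historical comparison.

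Optionally, record the most recent chart HbA1c before Visit 1 for a sensitivity analysis. It should usually exist, because "Our clinic standard is to have patients attend at least 4 visit per year". It is a partial remedy unless all measurements are equally correlated.

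**Cost.** A chart look-up to set the index visits (chart review is already planned for participants), fewer eligible historical controls, and a smaller apparent improvement. Enrolment is unchanged.

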- The care team member initiating the CGM will ask patients and their caregivers if they are interested in hearing about this study to understand the use of CGM in youth with type 2 diabetes
- If a patient and/or caregiver is interested in this study, one of the study team members will discuss the study with the participant and obtain informed consent and assent (if needed).
- Participants who consent to be part of this study will have the appropriate CGM applications and readers active (Libre 2 CGM, LibreView, LibreLink) as per standard clinical care.

1. Informed consent and assent - this can be done in person or virtually
2. CGM start – done by CDE in clinic
 - a. 4 weeks of supplies given – CRC to confirm with family preferred way to get supplies every 6 weeks and best way to contact them.
 - b. Standard clinic CGM education
3. Routine clinic visit

4. PRO completion - participants who speak and write English and Spanish will be asked to complete PROs surveys

Visits 2a,3a,4a,5a:

1. CRC check in with family/patient
 - a. Confirm CGM use
 - b. Address CGM issues – CRC to address or forward to CDE if clinical question
 - c. Ship or arrange for supply pick up (6 weeks of supplies)
 - d. Confirm next clinic visit

Visits 2,3,4,5,6:

[figure not shown]
1. Routine Clinic visit including CDE visit. The purpose of these visits is to reinforce prior teaching, answer questions, and review CGM data, making changes as necessary to the patient's care regimen to better control their diabetes.
2. CRC check in, supplies provided (for all visits except visit 6)
3. PRO questionnaires administered for visits 3 and 6

Biostatistical plan

Statistical methods: We will generate descriptive statistics for all participants included in the study and will create a STROBE diagram²⁶ to describe participants screened, recruited, and followed in both study phases. To address the feasibility of CGM use in T2D, we will estimate the proportion of participants who have sustained CGM use in both phase 1 and 2. Our feasibility analysis will include all participants. To address H1c, we will fit linear regression models using GEE to estimate the association of PROs with longitudinal HbA1c. Logistic regression models fit with GEE will be used to estimate the association of PROs with dichotomous diabetes management outcomes (e.g., presence of diabetes distress).

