At each visit we will collect descriptive data on CGM use, clinical glucose outcome metrics, and provide CGM supplies. Mixed affects modeling will be used to characterize the trajectory of measured variables and to account for patient-level correlation of this data. To account for gaps in CGM use we will use intention to treat analysis and consider a censoring method for a patient who leaves the practice or are lost to follow up. We will also perform an exploratory analysis of the relationship at a patient-level between days of CGM wear and time in range.

Study Timeline

Data Collection and Entry

1. Study participant data entry will be collected and entered in Stanford RedCap by the study team.
2. PRO will be collected in RedCap

The initial survey is filled out in person during the CGM visit during which, parents provide an email that will be the platform for contact for the future surveys. At the follow up points, the RedCap data base will automatically trigger survey link to the email on file. If the survey is not completed, a second email is sent as a reminder followed by provider team reminders. Participant data will be included for analysis for the time frames that are available when.

These measures will assess issues of adherence or illness distress and provide valuable information for providers to better understand the impact of early CGM initiation. The patient/guardian will have the option of filling out the questionnaires in English or Spanish. Based on the evidence in the PROs literature and our clinical experiences, we have developed an algorithm for responding to PROs screen scores that are outside of the normative range triggers a response from social worker and/or diabetes psychologist²⁷. Study personnel will complete a chart review to collect relevant health information including diagnosis, duration of disease, indicators of health status, and regimen information (e.g. medication, doses). These medical record data are required to assess the validity and usefulness of the clinical PROs screening measures. Additionally, reliability analysis will be conducted to examine the psychometric properties of the PROs measures, and the satisfaction questionnaire data will be aggregated to assess the acceptability of the PROs procedure from the patient's perspective.

- PROMIS global health (youth): BELOW 22 for the PROMIS global health scale. Anyone who scores 21 or lower would trigger an alert to place a diabetes psychology referral.

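### The protocol does not ensure that the first PRO survey comes before CGM start, and its listed Visit 1 order puts it after

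*Combined protocol and SAP*

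**What the plan says.** Under Procedures and Methods, Visit 1 is described twice. The bullets run: CGM is offered at the scheduled clinic visit; a diabetes educator gives CGM education; then "The care team member initiating the CGM will ask patients and their caregivers if they are interested in hearing about this study"; and those who are interested go on to consent. The numbered steps run: (1) "Informed consent and assent - this can be done in person or virtually"; (2) "CGM start – done by CDE in clinic", with 2b reading "Standard clinic CGM education"; (3) a routine clinic visit; (4) "PRO completion - participants who speak and write English and Spanish will be asked to complete PROs surveys".

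The schedule table marks consent, CGM start, CGM education and PROs all at Visit 1 and gives no order within the visit. Data Collection and Entry says: "The initial survey is filled out in person during the CGM visit". PROs are repeated at Visits 3 and 6.

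On what the surveys are for, H1c in Specific Aims states that "it is expected that diabetes-specific distress will decline, and overall well-being/quality of life will improve". It also uses PROs collected at baseline as predictors of HbA1c and diabetes management outcomes.

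**The concern.** A statement that distress falls and quality of life improves with CGM needs a value from before CGM begins. All participants receive CGM, and the historical controls of Aim 2 are named for HbA1c, time in range and time in hypoglycemia, not for PROs. The first survey is therefore the only reference for PRO change. It also anchors any trajectory fitted to the PROs under the planned mixed models.

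If the survey is completed after education, sensor placement and the clinic encounter, any immediate response to them (relief, or worry about a new device) becomes part of the baseline. The technology survey asks about diabetes devices, so device training just beforehand bears on it most directly, although H1c states no expected change for that survey. Phase 2 follows its new cohort at a similar cadence, so the same weakness could carry over.

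**Working it through.** There is no stated figure to reproduce: the plan gives no PRO effect size, PRO standard deviation or sample-size calculation for H1c. The check compares the places that bear on order and then uses one line of algebra.

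**Order of events, source by source**

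| Source | What it fixes about the first PRO survey |
|---|---|
| Visit 1 numbered steps | Listed fourth, after consent (1), CGM start and education (2, 2b) and the clinic visit (3) |
| Visit 1 bullets | Surveys not mentioned; education is listed before the study is introduced and consent obtained |
| Schedule table | Same visit as CGM start and education; no order |
| Data Collection and Entry | Same visit as CGM start; no order |

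The two Visit 1 lists disagree: the bullets put education before consent, the numbered steps put consent before education. They cannot both be strict sequences. Take each in turn.

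- Numbered steps followed: the survey comes after education, sensor placement and the clinic visit.
- Bullets followed: education precedes consent. The Recruitment paragraph requires consent before the study begins, so study surveys follow consent and hence also follow education. The bullets do not settle whether the sensor is already on.

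Neither list yields a survey before education, and no text requires one before sensor placement.

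**Effect on the change estimate**

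Let B be a participant's score before any Visit 1 procedure, s the shift caused by same-day procedures, and F the score at follow-up.

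- First survey recorded: B + s
- True change: F − B
- Observed change: F − (B + s) = (F − B) − s

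The bias in the mean change is minus the mean of s, one for one. It does not depend on the number of participants, so going from 30 in phase 1 to 50 in phase 2 does not reduce it. If only a fraction p of participants complete the survey after the procedures, with mean shift s among them, the bias is −p × s.

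Direction, for a distress score where higher is worse:

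- s below zero (relief): a real decline is understated.
- s above zero (worry or burden): a decline is overstated.
- s = 0, or survey done first: no bias.

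**Effect on the association analysis**

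The Biostatistical plan assigns to H1c a GEE model of PROs against longitudinal HbA1c. A shift common to all participants moves the intercept of a linear model and leaves the slope unchanged. Only a shift that varies between participants could affect the slope. Baseline HbA1c is not affected.

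**The case against.** The strongest reply is that the numbered steps are a checklist. Nothing says they must be carried out in that order, and their conflict with the bullets suggests that they were not written as a sequence. The protocol also says that data collectors follow a written procedure for the measures, and survey timing may be set there. This stands as far as it goes. A reader might infer from the list that the first PRO value is definitely post-intervention; the documents do not support that, because the order is listed but not mandated. The reply still does not produce a protected baseline, since both lists put education ahead of the surveys.

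A second reply is that exposure is slight. Even in the listed order the first survey falls on the day of CGM start, before any sustained wear, and the instruments ask about quality of life, diabetes burden and general health. This also stands: the documents contain no evidence that same-day placement or education moves these scores. A reader might want to attach a number to the bias, but the plan gives no basis for any value of s, and zero is compatible with everything in it. Nor can one say that participants have already had their glucose control reviewed when they answer. For Visit 1 the text says only that a routine clinic visit takes place; review of CGM data is described for Visits 2 to 6.

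Third, this is an uncontrolled pilot about feasibility, with PROs last of five measured outcomes, and the analysis named for H1c is an association model. That lowers the severity. It does not remove the point, because H1c states an expected direction of change and the first survey is its only reference.

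**Conclusion.** The point holds in a limited form. The protocol does not ensure that the first PRO survey precedes CGM start and education, and its listed order puts the survey after both. The change part of H1c is exposed to a one-for-one bias of −s, with s unknown in size and direction and possibly zero. The association of PROs with HbA1c is little affected.

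This rests on two assumptions: that study surveys are completed only after consent, and that no separate procedure already places them before sensor placement. If surveys are in practice done first, only the wording needs correcting. Severity is minor, but the improvement is cheap and worth making before enrolment, because a pre-CGM value cannot be recovered once a participant has started.

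**What to change.** 1. Reorder the Visit 1 steps so that PROs are completed after consent and before sensor placement. Where consent timing permits, place them also before CGM education and the clinic encounter. Virtual consent is already allowed and makes this feasible without an added visit.
2. Reconcile the Visit 1 bullets with the numbered steps, so that consent, surveys, education and CGM start appear in one consistent order.
3. Record the survey completion time relative to CGM start.
4. Flag any baseline survey completed after placement, and repeat the PRO change estimates without the flagged surveys as a sensitivity analysis.

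If the order cannot be changed, report the first value as a day-of-CGM-start measurement and not as a pre-CGM baseline.

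The cost is small but not nil: visit flow changes slightly, and because the bullets have the staff member starting CGM introduce the study after education, the consent conversation would have to move earlier for some families. No new instrument or visit is needed.
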